### 14.1.2. Adverse Events Leading to Withdrawal

A data listing of AEs leading to withdrawal will be provided, displaying details of the event(s) captured on the CRF.

### 14.1.3. Serious Adverse Events

A data listing of SAEs will be provided, displaying details of the event(s) captured on the CRF. Serious adverse event narratives will be provided for the CSR by MediciNova.

#### 14.1.4. Deaths

If any subject dies during the study, relevant information will be supplied in a data listing, and appropriate SAE narratives.

### 14.2. Pregnancies

Pregnancy data will be shown in a data listing. No special analysis will be performed on the pregnancy data. Subjects are to be discontinued from the study if they become pregnant.

### 14.3. Clinical Laboratory Evaluations

For numerical lab measurements values below the lower detection limit or above the upper detection limit (indicated in the database as  $\langle xx, \rangle xx, \rangle xx$ ) will be replaced by the detection limit (i.e. xx). Measurements resulting in negative numbers will be set to missing.

Descriptive statistics of measurements will be presented for clinical laboratory values, by treatment arm, phase and visit. Descriptive statistics of changes from baseline will be presented for clinical laboratory values, by treatment arm, phase, and visit.

Categorical lab measurements will be tabulated by treatment arm and visit.

Parameters will be grouped as:

- Blood Chemistry Tests
- Haematology tests
- Urinalysis Tests

Lab shift tables presenting the incidence of new or worsening clinically significant findings from baseline to the last visit will be displayed by treatment arm, for DBT and OLE phase respectivel. For this, a shift table will be created by phase, treatment arms and parameters with the following categories: "CS Low", "NCS Low", "Normal", "NCS High".

Shift from baseline to the highest lab value, and from baseline to the lowest lab value will also be displayed, for the DBT and OLE periods respectively. To create this shift table, change from baseline to the highest and lowest values will be calculated for every subjects within DBT and OLE periods, respectively. Descriptive statistics of these change from baseline values will be presented by phase, treatment arms, parameter and change from baseline category (Cfb to lowest, Cfb to highest). A bysubject listing of these change fom baseline values will be provided.

Incidence of out-of-normal-range values and markedly abnormal change from baseline in laboratory safety test variables will be tabulated by treatment arm and phase. A markedly abnormal change from baseline value is defined as any value larger than three times the upper normal limit.

Laboratory values that are outside the normal range, and their clinically significance will be flagged in the data listings. A by-subject listing of all subjects with abnormal laboratory values will be provided.

Statistical Analysis Plan v1.0

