4.2. Prior Clinical Experience

4.2.1. Clinical Study Overview

To date, a total of 11 clinical trials have been conducted with MN-001 and over 600 subjects have been dosed. Single and multiple doses of MN-001 ranging from 80 mg to 2000 mg for up to 12 weeks in 6 Phase 1 trials, 4 Phase 2 trials and 1 Phase 3 trial have been evaluated in healthy subjects and patients with asthma and interstitial cystitis. A summary of completed trials is provided in Table 5.

Phase 1 Studies

In the single dose studies of 80 mg to 600 mg, there appeared to be few adverse events. The most common treatment emergent adverse events (TEAEs) were mild diarrhea, sensation of

borborygmus, and heavy headedness. No clinically significant changes in vital signs, ECGs, and safety labs were observed.

In two multi-dose studies (Study KCA-757 and Study 478-02), MN-001 250 mg to 1000 mg bid was administered for approximately 7 days in healthy volunteers and subjects with mild bronchial hypersensitivity. No serious adverse events were reported and no subjects discontinued the study due to an adverse event. The most common AEs experienced in study 478-02 were upper abdominal pain (reported by 1 subject each in the 500 mg and 750 mg groups), loose stools (reported by 1 subject each in the 500 mg and 1000 mg groups), and nausea (reported by 1 subject each in the 750 mg and 1000 mg groups). The Investigator considered the following treatment-emergent AEs to be possibly or probably related to study drug (treatment group in parentheses): abdominal pain (placebo), upper abdominal pain (500 mg and 750 mg), dyspepsia (1000 mg), fatigue (placebo), loose stools (500 mg and 1000 mg), nausea (750 mg and 1000 mg), somnolence (750 mg), urine odor abnormal (500 mg).

In study 478-02, vital signs were within normal limits. All mean ECG measurements remained within normal limits. At Hour 359.67 mean QTc for the 750 mg group increased 27.66 ms from baseline for a mean QTc of 395.83 ms and mean heart rate increased 14.50 bpm from baseline for a mean heart rate of 70.67 bpm. No other marked mean changes from baseline were noted. The Investigator considered none of the ECG abnormalities in this study to be adverse events.

All treatment groups, including the placebo group, exhibited notable mean increases in CPK (ranging from approximately 22 to 135 U/L) at Hour 360. No other marked mean changes from baseline were noted for the remaining serum chemistry parameters.

High Doses of MN-001 (1500 mg/day)

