8.8.1.1. Screening Phase (Up to 3 months prior to Day 1)

Visit 1 (Day -90 to Day -8)

At any point during this time, subject may be approached for participation in the study. An informed consent form (ICF) will be given to the subject and the subject will be instructed to read the ICF and ask the study staff any questions they may have. The subject can either sign the ICF then or defer signing until they return for Study Visit 2.

Visit 2 (Day- 7 ± 5 days)

During the Screening Phase, once the informed consent form is signed, the following assessments will be performed/collected):

- Inclusion/Exclusion criteria review
- Medical history
- Physical examination
- Height/body weight
- Vital signs including supine blood pressure, respiratory rate, heart rate, and temperature
- 12 lead Electrocardiogram (ECG)
- Fasting safety labs chemistry (including CPK, liver enzymes, lipid panel) hematology, and urinalysis labs

- Serum β-hCG (pre-menopausal females)
- Blood Sample for biomarker
- Prior/concomitant medication review
- Pulmonary function test
- 6 minute-walk test (6MWT)*
- Dyspnea score (MMRC: Modified Medical Research Council Dyspnea Score)
- ATAQ-IPF (A Tool to Assess Quality of Life in IPF)

The results of pulmonary function test, 6MWT, MMRC and ATAQ-IPF at this visit are considered "Baseline" values.

* Two tests should be performed for 6MWT

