13.1.4. Safety Analysis

Safety analyses will be conducted on the Safety Analysis Set.

The incidence of treatment-emergent AEs (TEAEs, defined as AEs occurring from the time of first dose through 7 days after the last dose of study medication), SAEs and AEs leading to discontinuations will be summarized by treatment group. Incidence of TEAEs will also be summarized by severity (mild, moderate, or severe), as well as by relationship to treatment (not related, possibly related, or probably related) and by seriousness.

Changes from baseline in laboratory values will be summarized by treatment groups for continuous variables. Lab shift tables showing incidence of new or worsening clinically significant findings from baseline to the last visit will be displayed by treatment groups. Shift from baseline to the highest lab value, and from baseline to the lowest lab value will also be displayed.

Incidence of out-of-normal-range values and markedly abnormal change from baseline in laboratory safety test variables will be tabulated by treatment group.

Changes in vital signs from baseline to each visit will be summarized by treatment groups.

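### SAP 14.3: the shift table for clinically significant laboratory findings has no CS High category, and the rule for a markedly abnormal change is ambiguous and one-sided

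*SAP*

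**What the plan says.** Protocol 13.1.4 asks for two laboratory tabulations that matter here. The first is "Lab shift tables showing incidence of new or worsening clinically significant findings from baseline to the last visit", by treatment group. The second is the incidence of out-of-range values and of "markedly abnormal change from baseline in laboratory safety test variables will be tabulated by treatment group". The protocol gives no threshold for a marked change and restricts neither table to high or low results.

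SAP 14.3 takes up both. It plans "Lab shift tables presenting the incidence of new or worsening clinically significant findings from baseline to the last visit", by arm and separately for the double-blind and open-label phases, and gives the categories as "CS Low', 'NCS Low', 'Normal', 'NCS High". For the second table it supplies the only definition in either document: "A markedly abnormal change from baseline value is defined as any value larger than three times the upper normal limit".

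The same section also provides that "Laboratory values that are outside the normal range, and their clinically significance will be flagged in the data listings". SAP 15, which lists departures from the protocol, mentions neither of these two rules.

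**The concern.** The shift table exists to count clinically significant findings, but its list names a clinically significant level on the low side only. The high side is plainly in scope, because a non-significant high category is listed. An elevation judged clinically significant has nowhere to go.

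The marked-change rule is named after a change but worded as a fixed multiple of the upper limit. The sentence does not settle whether that multiple applies to the post-baseline measurement or to its difference from baseline, and two programmers could reasonably produce different counts from it. It also contains no criterion for decreases, although it applies to the laboratory safety variables generally, haematology included.

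Safety and tolerability is a secondary objective, and laboratory values are a named part of its assessment (protocol 11, SAP 5.2.2). At stake is whether these two by-arm tables show what their titles say.

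**Working it through.** The plan has no figure to reproduce here. The check sets the stated purpose of each table against its rule.

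**Shift table**

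Inputs: the purpose and the category list, both from SAP 14.3, and the matching purpose in protocol 13.1.4.

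- A list covering both directions and both levels of significance, plus normal, has five members: CS Low, NCS Low, Normal, NCS High, CS High.
- The SAP lists four. The missing one is CS High.
- For each parameter, arm and phase, the table has 4 × 4 = 16 cells instead of 5 × 5 = 25. The 25 − 16 = 9 missing cells are every transition into or out of CS High, plus CS High at both times.
- The SAP does not say how an unlisted result would be handled. If it were placed in NCS High, a worsening from NCS High to CS High would appear as no change.

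**Marked-change rule**

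Input: the 3 × ULN definition in SAP 14.3. Let b be the baseline value and v the later value, both in multiples of ULN. The pairs below are assumed for illustration and are not trial data.

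- Measurement reading: counts if v > 3.
- Change reading: counts if v − b > 3.

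| b → v | v − b | Measurement reading | Change reading |
|---|---|---|---|
| 3.2 → 3.2 | 0 | counts | does not count |
| 6.0 → 3.2 | −2.8 | counts, though improving | does not count |
| 0.5 → 2.9 | +2.4 (2.9/0.5 = 5.8-fold) | does not count | does not count |
| 0.5 → 3.4 | +2.9 (3.4/0.5 = 6.8-fold) | counts | does not count |
| 0.8 → 0.05 | −0.75 | does not count | does not count |

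The first, second and fourth rows are classified differently by the two readings, so the incidence depends on a choice the SAP does not make. On the change reading, a subject starting at 1.0 must exceed 1.0 + 3 = 4.0.

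The low side does not depend on the illustrations. A value below the lower limit of normal is below the upper limit, so v < 1 and the measurement reading fails. A fall has v − b < 0, so the change reading fails. No marked decrease to a low value can count on either reading.

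**The case against.** The missing category is probably a drafting slip. The governing sentence has no direction, NCS High is listed, and the section has other typing errors. Loss in conversion from PDF cannot be strictly excluded, but the list is a complete sentence with no visible gap. If it is a slip, the correction is still needed.

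The strongest objection concerns coverage, and most of it stands. Protocol 12.1 makes a clinically significant abnormal laboratory finding an adverse event. Protocol 11 and SAP 5.2.2 name laboratory treatment-emergent events as a safety measure. SAP 14 lists them as a summary category, and SAP 14.1.1 tabulates treatment-emergent events by arm and phase. SAP 14.3 adds out-of-range incidence, changes to the lowest and highest value, and listings. A reader might infer that clinically significant elevations would go unreported; the documents do not support that. What none of these outputs replaces is the by-arm, parameter-level shift from baseline to last visit by clinical significance.

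A reader might also infer that the marked-change rule flatly ignores baseline. That goes too far. The preceding paragraph of SAP 14.3 uses the same phrase for computed differences, so the change reading has textual support. The sound criticism is ambiguity. Nor does the one-sided rule contradict the protocol, which sets no threshold and no two-sided requirement. Falls still appear as out-of-range values and in the change to the lowest value. But the rule is still blind to marked decreases in the one table titled for marked change.

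Finally, a reader might point to protocol 4.2.1, where the groups in an earlier multiple-dose study "exhibited notable mean increases in CPK (ranging from approximately 22 to 135 U/L) at Hour 360". Those increases occurred in every group, placebo included, and are not called clinically significant. They are not evidence of a drug effect and do not measure the impact of the missing category.

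**Conclusion.** Wrong as written, with minor impact. The shift table cannot show a new or worsening clinically significant elevation. The marked-change rule is ambiguous about baseline and cannot count a marked decrease to a low value on either reading. The first conclusion rests on the printed category list being complete. The second follows from the wording alone.

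The size cannot be put as a number of subjects, because the documents give no laboratory event rates. It is tempting to express it as the share of an arm that one subject represents in a trial of about 15, but that share would be the same for any table in this trial and says nothing about how often the problem would arise.

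The effect is confined to the descriptive tabulation of laboratory data. No hypothesis test, efficacy endpoint or adverse-event proportion changes, and the stopping rules in protocol 7.3 work from graded adverse events, not from these tables.

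**What to change.** In SAP 14.3, before treatment codes are opened:

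1. Add CS High to the shift-table categories.
2. State whether the value in the marked-change definition is the measurement or the change from baseline.
3. Either relabel that item as values above 3 × ULN, or define it relative to baseline with a criterion for decreases where relevant. The sponsor sets the limits.

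The cost is one added category and one or two reworded sentences. Clinical significance is already to be flagged in the listings, so no new data should be needed. SAP 3 places final approval before unblinding, so the wording can be settled without knowledge of the results by arm.

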### 14.4. Hemodynamics (Vital Signs)

Descriptive statistics of actual values and changes from baseline will be calculated for SysBP, DiaBP, HR and Respiratory rate and Temperature. These summaries will be presented by treatment arm, phase and visit.

All vital sign measurements will be listed.

### 14.5. Body weight

For body weight, descriptive statistics will be prepared by treatment arm, phase, and visit.

All weight measurements will be listed.

### 14.6. ECGs

Descriptive statistics will be presented for ECG measures of PR interval, QRSD interval, QT interval, QTc interval (Fridericia's method), and HR. These statistics will be presented by treatment arm, phase and visit.

The number and percentage of subjects with normal and abnormal ECG results will be summarized by treatment arm, phase and visit. All ECG measurements will be listed.

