#### 4. PREFACE

This Statistical Analysis Plan (SAP) describes the planned analysis and reporting MediciNova Inc. protocol MN-001-IPF-201 (A Randomized, Placebo-Controlled, Double-Blind Six-Month Study Followed by an Open-Label Extension Phase to Evaluate the Efficacy, Safety and Tolerability of MN-001 in Subjects with Idiopathic Pulmonary Fibrosis (IPF)). This phase 2a study is being completed to assess the safety, tolerability, and efficacy of MN-001 for the treatment of IPF in male and female subjects  $\geq 21$  and  $\leq 80$  years of age with a confirmed diagnosis of moderate to severe IPF. The following documents were reviewed in preparation of this SAP:

- Clinical Study Protocol MN-001-IPF-201 and amendment 1 issued 15APR2015.
- Case report forms (CRFs) for Protocol MN-001-IPF-201.
- ICH E9: Guidance on Statistical Principles for Clinical Trials.
- ICH E3: Guideline for the format and content of the clinical and statistical sections of an application
- ICH E14: Clinical evaluation of QT/QTc interval prolongation and proarrhythmic potential for non-antiarrhythmic drugs

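### SAP 14.6 plans no ECG change from baseline and no QTcF category counts, although an ECG baseline is defined and the protocol reports an earlier QTc rise that appeared only as a change

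*SAP*

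**What the plan says.** SAP 14.6 is the only ECG analysis in either document: "Descriptive statistics will be presented for ECG measures of PR interval, QRSD interval, QT interval", followed by QTcF and heart rate, per arm, phase and visit. It adds counts of normal and abnormal ECGs and a listing of all values. SAP 10 defines descriptive statistics to include the SD, quartiles, minimum and maximum.

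Other safety data are handled differently. For vital signs, SAP 14.4 says "Descriptive statistics of actual values and changes from baseline will be calculated for SysBP" and the other parameters, and SAP 14.3 plans change from baseline and shift tables for laboratory values. SAP 10.3 sets the ECG baseline at Visit 2. SAP 4 lists "ICH E14: Clinical evaluation of QT/QTc interval prolongation and proarrhythmic potential for non-antiarrhythmic drugs" among the documents reviewed.

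On earlier ECG data, Protocol 4.2.1 says of study 478-02: "At Hour 359.67 mean QTc for the 750 mg group increased 27.66 ms from baseline for a mean QTc of 395.83 ms", and in the same sentence "mean heart rate increased 14.50 bpm from baseline for a mean heart rate of 70.67 bpm". It also says that mean ECG measurements stayed within normal limits, that "No other marked mean changes from baseline were noted" and that "The Investigator considered none of the ECG abnormalities in this study to be adverse events". Table 4 shows bid dosing in that study. For CL-003, which gave 750 mg bid and 500 mg tid, the protocol reports no clinically significant ECG change. SAP 10.1 defines the active arm as 750 mg twice daily.

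**The concern.** The 478-02 result shows what a table of raw values can hide. By absolute value the 750 mg group was normal; the rise appeared only against baseline. SAP 14.6 keeps the absolute view and a normal/abnormal count, and leaves out the change view, for a regimen that includes the same dose and frequency.

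Safety is a secondary objective, Protocol 11 promises statistical as well as clinical review of ECGs, and the results are meant to inform later studies. A later design team would want the mean within-subject QTcF change, its SD and the largest individual changes. None of these is a planned output.

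**Working it through.** The plan has no ECG sample-size or power figure to reproduce. The checks below ask what the earlier result amounts to, what the planned tables can show, and what the added tables would show.

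**1. The 478-02 figure (Protocol 4.2.1).**
- Implied baseline QTc = 395.83 − 27.66 = 368.17 ms. Implied baseline heart rate = 70.67 − 14.50 = 56.17 bpm.
- RR = 60/HR: 60/56.17 = 1.068 s before and 60/70.67 = 0.849 s after.
- The correction formula is not named. Take QT = QTc × RR^k on the group means, with k = 1/3 (Fridericia) or 1/2 (Bazett).
- If Fridericia: QT goes from 376.4 to 374.8 ms, and the QTcF rise is 27.66 ms.
- If Bazett: QT goes from 380.5 to 364.7 ms. Converted to Fridericia, 372.2 goes to 385.2 ms, a rise of 12.9 ms.
- On the SAP's QTcF scale the rise is therefore about 13 to 28 ms, depending on the formula.
- Hour 359.67 is 359.67/24 = 15.0 days, while the text gives about 7 days of dosing and Table 4 gives 6. Its timing relative to dosing is unclear.

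**2. What the planned raw means can show.** Inputs: about 15 subjects at 2:1, so about 10 on MN-001. Assumed between-subject SD: 15 to 25 ms.
- SE of one visit mean = SD/√10 = 4.7 to 7.9 ms.
- SE of the difference between two visit means, treated as independent = √2 × that = 6.7 to 11.2 ms.
- A 27.66 ms shift is 4.1 to 2.5 of these SEs. A 12.9 ms shift is 1.9 to 1.2.

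A group rise of the full reported size would show in the planned means. One at the lower end might not stand out.

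**3. What the raw table leaves out.** With the same subjects at both visits and equal SDs, the difference of means equals the mean change, but the SD of change is SD × √(2(1 − ρ)), where ρ is the within-subject correlation. The planned summaries do not give ρ. For an assumed SD of 20 ms:

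| assumed ρ | SD of change | SE, n = 10 |
|---|---|---|
| 0 | 28.3 ms | 8.9 ms |
| 0.5 | 20.0 ms | 6.3 ms |
| 0.8 | 12.6 ms | 4.0 ms |

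The spread of change thus cannot be recovered from the summary table. If subjects drop out, the difference of visit means also compares different sets of people.

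**4. Individual rises.** The only QTcF limit in the documents is the 450 ms exclusion criterion. A subject starting at 368.17 ms could rise by 450 − 368.17 = 81.83 ms before passing it. The tabulated maximum shows whether anyone passed 450 ms, but not a large rise below that level.

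**5. What added categories would show.** Assume 10 subjects, normal changes, a true mean rise of 27.66 ms, and illustrative cuts of +30 and +60 ms (not from the documents). P(at least one) = 1 − (1 − p)^10.

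| category | assumed SD | P(at least one of 10) |
|---|---|---|
| change > 30 ms | 10 to 25 ms | 0.995 to 0.998 |
| change > 60 ms | 10 to 25 ms | 0.01 to 0.64 |
| value > 450 ms, mean 395.83 ms | 15 to 25 ms | 0.002 to 0.14 |

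With a true rise of 12.9 ms, the first row becomes 0.36 to 0.94. The change table is therefore the essential part; a 450 ms count alone would usually stay empty.

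**6. Precision.** The 95% half-width for the arm difference in mean change is t(0.975, 13) × SD × √(1/10 + 1/5) = 2.16 × SD × 0.548, or 11.8 to 29.6 ms for an assumed SD of 10 to 25 ms.

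**The case against.** The strongest reply is that little is lost. The full reported rise would be visible in the planned means (step 2), maxima are tabulated, and every ECG value is listed for about 15 subjects, so changes can be worked out by hand. Protocol 8.8.2.6 requires clinically significant post-dose ECG changes to be recorded as adverse events, and Protocol 6.3 has an independent safety monitor reviewing data in both phases. Protocol 13.1.4 asks for change from baseline in laboratory values and vital signs but not ECGs, so 14.6 does not depart from the protocol. SAP 14.5 also omits change for body weight. ICH E14 is listed as reviewed, which is not a commitment to a particular table.

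All of that stands, and it limits the size of the point. It does not supply the paired summary. A listing leaves the change calculation to each reader, and adverse event recording depends on someone noticing a change that may lie within normal limits.

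A reader might infer more: that MN-001 has a known QTc signal which this plan would miss, and that ECGs were timed at 1.5 h to look for it. The documents do not support this. The rise was one group at one time point, with a concurrent heart-rate rise and an unnamed formula; no other marked mean change was noted, although 1000 mg bid was also given; CL-003 showed no clinically significant change. Neither document gives a reason for the 1.5 h timing.

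**Conclusion.** The omission is real and is a modest reporting gap. SAP 14.6 has no ECG change from baseline and no QTcF categories, nothing elsewhere supplies them, and the baseline needed is already defined. The protocol's one reported QTc rise (27.66 ms as stated, about 13 to 28 ms on the Fridericia scale) lay within normal limits, so a normal/abnormal count would probably not have flagged it.

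The plan would not be blind to a large group shift. What is missing is the paired change, its spread, and large individual rises within the normal range. The omissions and the reported figures come straight from the documents. The SDs, correlations and the +30 and +60 ms cuts are assumptions, and the Bazett conversion applies an individual-level formula to group means.

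**What to change.** Add two tables to SAP 14.6:

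1. Descriptive statistics of change from baseline in QTcF, PR, QRS and heart rate, per arm, phase and visit.
2. Counts of subjects with QTcF above 450 ms (the entry limit, used only as a descriptive cut) and in QTcF change categories that the sponsor chooses and writes into the SAP before unblinding.

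State the baseline for each phase. For the double-blind phase use Visit 2. For former-placebo subjects in the open-label extension follow SAP 10.3 (Visit 8), once a conflict is reconciled: SAP 10.3 treats Visit 8 values as taken before the first MN-001 dose, while Protocol 8.8.1.2 places the Month 6 ECG 1.5 h post dose and has all subjects taking MN-001 from that visit. Footnote e of Protocol Table 1, under which open-label drug is dispensed only after all assessments, needs to be read together with these. The SAP should say which dose precedes that ECG.

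The cost is two descriptive tables from data already collected. At about 10 versus 5 subjects they will be imprecise (step 6) and should be read descriptively, as SAP 10.6 already requires for all tests. If the codes have been broken, SAP 3.2 still allows the tables, identified in the study report as unplanned.
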